3.3 Randomization

Not applicable.

3.4 Blinding

This is an open-label study.

3.5 Determination of Sample Size

Up to approximately 750 subjects will be enrolled. The sample size for this study is not based on statistical power, but will depend on the number of subjects who transition into this OL extension study from the antecedent study.

3.6 Coronavirus Disease 2019

In March, 2020, the emerging coronavirus disease 2019 (COVID-19) pandemic resulted in implementation of urgent safety measures designed to ensure subject safety. Mechanisms to record information on the potential impact of the COVID-19 pandemic on data itself, as well as data collection and integrity, were implemented (as detailed in the Data Management Plan [DMP] Appendix B). Recruitment efforts into the antecedent study (ACP-103-046), and roll-overs into the open-label extension study (ACP-103-047), were paused. The impact of COVID-19 on statistical analysis is discussed in each of the relevant sections of this SAP.

4 ANALYSIS SETS

4.1 Enrolled Subjects

Enrolled subjects are defined as those subjects who signed informed consent (from either the subject or legally accepted representative) for Study ACP-103-047, excluding rollover failures. Data listings will include all enrolled subjects.

4.2 Safety Analysis Set

The Safety Analysis Set will include all enrolled subjects who have taken at least 1 dose of OL study drug. The Safety Analysis Set will be used for all analyses.

5 DATA HANDLING CONVENTIONS

All data collected in this study will be listed.

5.1 General Data Reporting Conventions

For continuous variables, the following summary statistics will be provided: number of subjects, mean, standard error of the mean (SE), standard deviation (SD), minimum,

maximum, and median. Unless specified otherwise, means, medians, and confidence intervals will be presented to one more decimal place than the raw data, and the SDs and SEs will be presented to 2 more decimal places than the raw data.

For categorical variables, summaries will include the number and percentage of subjects in each category, using the number of subjects with non-missing values as the denominator for the percentages (unless otherwise specified). Categories with zero counts will not have zero percentages displayed. Percentages will be presented to 1 decimal place.

When converting number of days to months, it will be calculated as the number of days divided by 365.25 and then multiplied by 12. When converting number of days to years, it will be calculated as the number of days divided by 365.25.

All endpoints will be summarized using the Safety Analysis Set.

No hypothesis testing is planned. Descriptive summaries of all safety and efficacy endpoints will be provided.

5.2 Treatment Cohorts

Summaries by cohort based on the antecedent study treatment group will also be provided. The cohorts are defined as follows:

- Cohort 1: DB placebo – OL pimavanserin
- Cohort 2: DB pimavanserin – OL pimavanserin

The DB treatment group will be based on the treatment actually received in the antecedent study, in the event that it is different from the randomized treatment assignment.

For each continuous measure in safety and efficacy analyses, change from Baseline results will be presented in two ways:

- Using the Baseline from Study ACP-103-047 and reporting the changes across OL Study ACP-103-047 timepoints.
- Using the Baseline from the antecedent study and reporting changes (observed values) across the timepoints of both the antecedent study and the OL Study ACP-103-047.

5.3 Derived Variables

In general, all assessment scale total scores and subscores will be derived within the analysis datasets. In the event that total scores and/or subscores are also collected on the electronic case report form (eCRF), the derived values will be used for all analyses. Both the raw and derived total scores will be presented in data listings.

5.3.1 CGI-S

The CGI-S scale is assessed at Baseline, Weeks 2, 4, 8, 12, 16, 28, 40 and Week 52/ET visits.

The CGI-S is a clinician-rated, 7-point scale that is designed to rate the severity of the subject's neuropsychiatric symptoms at the time of assessment using the Investigator's judgment and past experience with subjects who have the same condition. The 7-point scores are: 1=normal, not at all ill; 2=borderline ill; 3=mildly ill; 4=moderately ill; 5=markedly ill; 6 =severely ill; 7=among the most extremely ill.

Missing CGI-S scores will not be imputed.

5.3.2 EQ-5D-5L Proxy Version 1

The EQ-5D-5L is assessed at Baseline, Week 12, Week 28, and Week 52/ET.

The EQ-5D-5L is a standardized instrument used as a measure of health outcome. The EQ-5D-5L Proxy version 1 will be used in this study. In this version, a caregiver (the proxy) is asked to rate the subject's health-related quality of life in their (the proxy's) opinion. The EQ-5D-5L consists of 2 components: the descriptive system, and the visual analogue scale (VAS).

The EQ-5D-5L descriptive system consists of 5 dimensions (mobility, self-care, usual activities, pain/discomfort, anxiety/depression) each of which has 5 potential responses. The responses record 5 levels of severity within a particular EQ-5D-5L dimension: 1=no problems; 2=slight problems; 3=moderate problems; 4=severe problems; 5=extreme problems. The responses for the 5 dimensions are combined into a single 5-digit code that describes the subject's health state.

The EQ-5D-5L VAS records the subject's health on a vertical visual analogue scale, where the upper endpoint is labeled "The best health you can imagine" and is numbered 100, while the lower endpoint is labeled "The worst health you can imagine" and is numbered 0. The EQ-5D-5L VAS will be treated as a continuous endpoint.

Missing values will not be imputed for either the EQ-5D-5L descriptive system or the VAS.

5.3.3 SDI

The SDI is assessed at Baseline, Week 12, Week 28, and Week 52/ET.

The SDI is an expanded version of one item of the Neuropsychiatric Inventory (NPI), consisting of the 7 subquestions from the NPI sleep disturbance item. Each of the subquestions was made into a separate question with frequency, severity, and caregiver distress rated by the caregiver with respect to the patient-participant for the 2 weeks prior to the visit. Thus, in contrast to a single rating for frequency and severity for all sleep

disturbance-related behaviors, which would be incorporated into an overall NPI score, the SDI score is derived after the caregiver rates the frequency and severity of each of the 7 separate sleep disturbance symptoms. Caregiver distress ratings are not part of the SDI total score, but distress is measured. The SDI total score is calculated as the average of seven frequency ratings \times average of seven severity ratings, with a range of 0-12.

If the frequency rating and/or the severity rating is missing for a single item, then the total score will be imputed as the average of the non-missing frequency ratings \times the average of the non-missing severity ratings. Otherwise, if more than one item has a missing frequency and/or severity rating, the total score will not be derived.

5.3.4 C-SSRS

The C-SSRS is assessed (when applicable) at Baseline, Weeks 2, 4, 8, 12, 16, 28, 40 and Week 52/ET visits.

The Columbia-Suicide Severity Rating Scale (C-SSRS) will be used to assess suicidal ideations and behaviors in subjects who are able to complete the assessment (subjects without dementia, defined as an $MMSE \geq 25$), and subjects with dementia who the Investigator has determined can complete the C-SSRS. The C-SSRS monitors changes in suicidal thinking and behavior over time, in order to determine risk. Four constructs are measured: the severity of ideation, the intensity of ideation, behavior, and lethality.

The C-SSRS version assessing information since the last visit will be completed at all visits (including the Baseline visit). The C-SSRS results for each subject should be reviewed by the Investigator at each visit. If at any time the C-SSRS results for a given subject reveal potential suicidality, then the Investigator should assess the clinical significance of such results. If a clinically significant risk of suicidality is identified for a subject, then the Investigator should discontinue the subject and implement appropriate treatment.

There are 5 questions about suicidal ideation, representing 5 types of suicidal ideation: wish to be dead; non-specific active suicidal thoughts; active suicidal ideation with any methods (not plan) without intent to act; active suicidal ideation with some intent to act, without specific plan; active suicidal ideation with specific plan and intent. If a subject answers “yes” to any of these 5 questions, this subject will be counted as having suicidal ideation.

There are 5 questions about suicidal behavior, representing 5 types of suicidal behavior: preparatory acts or behavior; aborted attempt; interrupted attempt; actual attempt; suicide. If a subject answers “yes” to any of these 5 questions, this subject will be counted as having suicidal behavior.

Missing C-SSRS item scores will not be imputed.

5.3.5 GCAS

The GCAS (when applicable) is assessed at Baseline, Weeks 2, 4, 8, 12, 16, 28, 40 and Week 52/ET visits.

If the subject is not able, in the Investigator's judgement, to reliably complete the C-SSRS the Global Clinical Assessment of Suicidality (GCAS) will be administered and used thereafter in the study. If the GCAS was used in the antecedent study, suicidality since last visit will be assessed at Baseline and at all other visits. The first assessment with the GCAS should assess lifetime suicidality and suicidality for the past 3 months, and at all other visits suicidality since the previous visit will be assessed.

The GCAS is a clinician-rated, 5-point scale that is designed to rate the subject's suicidality based on the report of the subject, the report of the study partner/caregiver, and the clinician's global assessment. Ratings are scored as follows: 0=absent; 1=feels life is not worth living; 2=wishes he/she were dead or any thoughts of possible death to self; 3=suicidal ideas or gesture; 4=attempt at suicide. The Investigator will record a subject rating, a study partner/caregiver rating, and a clinician rating.

Missing scores will not be imputed.

5.3.6 ESRS-A

The ESRS-A is assessed at Baseline, Weeks 2, 4, 8, 12, 16, 28, 40 and Week 52/ET visits.

The ESRS was developed to assess 4 types of drug-induced movement disorders (Parkinsonism, akathisia, dystonia, and tardive dyskinesia) with established reliability, validity, and sensitivity. The ESRS-A, an accepted modified form of the original ESRS, will be used during the study to monitor for any worsening in extrapyramidal symptoms or signs at scheduled and unscheduled visits.

The ESRS-A consists of 4 subscales and 4 clinical global impression movement severity (CGI-S) scales of Parkinsonism, dyskinesia, dystonia, and akathisia. Each item of the subscales and each CGI-S rating is scored on a 6-point scale with higher scores denoting more severe drug-induced movement disorders: 0=absent; 1=minimal; 2=mild; 3=moderate; 4=severe; 5=extreme.

The 4 ESRS-A subscales are defined as follows.

- Parkinsonism subscale: 10 items (minimum=0, maximum=50)
 - P1 Rigidity: Upper limbs
 - P2 Rigidity: Lower limbs
 - P3 Rigidity: Neck

- P4 Tremor: Face, jaw/chin, lips, head
- P5 Tremor: Upper limbs/hands
- P6 Tremor: Lower limbs/feet
- P7 Reduced facial expression/speech
- P8 Impaired Gait/Posture
- P9 Postural Instability
- P10 Bradykinesia/Hypokinesia
- Dystonia subscale: 6 items (minimum=0, maximum=30)
 - DT1 Tongue
 - DT2 Jaw
 - DT3 Eyes, upper face, lower face, larynx
 - DT4 Shoulders, upper limbs, hands
 - DT5 Hips, lower limbs, feet
 - DT6 Trunk, neck
- Dyskinesia subscale: 6 items (minimum=0, maximum=30)
 - DK1 Tongue
 - DK2 Jaw
 - DK3 Eyes, upper face, lower face
 - DK4 Shoulders, upper limbs, hands
 - DK5 Hips, lower limbs, feet
 - DK 6 Trunk, neck
- Akathisia subscale: 2 items (minimum=0, maximum=10)
 - A1 Objective (observed during patient examination)
 - A2 Subjective

The ESRS-A total score is calculated as the sum of the 24 item scores with a possible range of 0 to 120. If 4 or fewer items are missing, then the total score for a given subject and timepoint will be imputed as the mean of the non-missing items multiplied by 24 and rounded to the nearest integer. If more than 4 items are missing, the total score will not be derived.

Missing ESRS-A item scores, subscale total scores, and CGI-S scores will not be imputed.

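### Prorating the ESRS-A total across four unlike subscales can create false change when the missing items cluster in one subscale (minor)

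*SAP*

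**What the plan says.** SAP Section 5.3.6 divides the ESRS-A into four subscales: parkinsonism (10 items), dystonia (6), dyskinesia (6) and akathisia (2). Each item is "scored on a 6-point scale with higher scores denoting more severe drug-induced movement disorders", running from 0 to 5. On the total it says: "The ESRS-A total score is calculated as the sum of the 24 item scores with a possible range of 0 to 120".

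With no more than 4 items missing, the total is "imputed as the mean of the non-missing items multiplied by 24", then rounded to a whole number. With more than 4 missing it is not derived. No condition is set on how many of the missing items may come from one subscale. The section adds that item scores, subscale totals and the global movement ratings are not imputed.

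SAP Section 14.6.1 summarises the total and the four global movement ratings, as observed values and as change from Baseline. It does so once from the open-label Baseline and once from the double-blind Baseline of the antecedent study. Item and subscale scores appear only in listings. Neither document plans a count of prorated totals or a sensitivity analysis of the rule.

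**The concern.** Multiplying the mean of the 20 to 23 rated items by 24 treats every missing item as if it stood at the average of all the rated ones. That is reasonable when the items measure one thing at a similar level. Here they belong to four different movement disorders, and a subject may score well above 0 on one subscale and 0 on the others. A missing item from the raised subscale is then understated, and a missing item from a subscale at 0 is overstated.

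The scale is there to detect worsening of extrapyramidal symptoms. The total is the only summary built from its items, and no subscale table is planned that would show an artefact. If the missing items differ between Baseline and a later visit, part of the reported change comes from which items were not rated.

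**Working it through.** **The plan's own figures.** Items: 10 + 6 + 6 + 2 = 24. Range: 50 + 30 + 30 + 10 = 120 = 24 × 5. Both match SAP 5.3.6.

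**What the rule does.** Let m items be missing. Before rounding,

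prorated total = 24 × (mean of rated items) = (sum of rated items) + m × (mean of rated items).

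The true total is (sum of rated items) + m × (mean of the missing items, had they been rated). So

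error = m × (mean of rated items − mean of missing items).

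The error is zero when the two means agree, for example when all 24 items are equal. The error in a change score is the error at the later visit minus the error at Baseline. It vanishes if the same items are missing at both visits and symptoms are stable.

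**Assumed profile A:** 3 on all 10 parkinsonism items, 0 elsewhere, true total 30. The profile is an assumption; the documents give no item scores.

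| Missing items | SAP rule | Error | Prorated within subscale, at least half rated |
|---|---|---|---|
| 4 parkinsonism | 18/20 × 24 = 21.6 → 22 | −8 | 3 × 10 = 30 |
| Gait and postural instability | 24/22 × 24 = 26.2 → 26 | −4 | 3 × 10 = 30 |
| 1 parkinsonism | 27/23 × 24 = 28.2 → 28 | −2 | 30 |
| 1 dystonia | 30/23 × 24 = 31.3 → 31 | +1 | 30 |
| 3 dystonia | 30/21 × 24 = 34.3 → 34 | +4 | 30 |
| 4 dystonia | 30/20 × 24 = 36 | +6 | not derived (2 of 6 rated) |

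**Milder profile:** 2 on all parkinsonism items, 0 elsewhere, true total 20. Four parkinsonism items missing: 12/20 × 24 = 14.4 → 14 (−6). Four dystonia items missing: 20/20 × 24 = 24 (+4).

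**Akathisia only:** both items 3, true total 6. Both missing: 0/22 × 24 = 0 (−6). The within-subscale rule would not derive this total.

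**Random missingness, milder profile.** Over all patterns of 1, 2 or 4 missing items among the 24, the mean prorated total before rounding is 20.0. Rounding moves it to between 20.1 and 20.2. The SD of the rounded total is 1.0, 1.7 and 2.3 points respectively. The rule then adds noise but essentially no bias.

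**Group level, milder profile.** The table shows the shift in mean change if a share of subjects has the four-item pattern after Baseline only.

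| Share of subjects (assumed) | 4 parkinsonism missing | 4 dystonia or dyskinesia missing |
|---|---|---|
| 1% | −6 × 0.01 = −0.06 | 4 × 0.01 = +0.04 |
| 5% | −0.3 | +0.2 |
| 10% | −0.6 | +0.4 |
| 20% | −1.2 | +0.8 |

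**The case against.** - **No evidence of frequency.** Neither document gives item scores or a missing-item rate, and profile A with four missing items is an unfavourable case. With one item missing the error is only −2 or +1. This stands, and it limits the point to what the rule can do.
- **Other measures are unaffected.** The four global movement ratings are not imputed and are summarised beside the total. Extrapyramidal adverse events enter the primary TEAE tables. Item scores are listed, so an affected total can be traced. SAP 5.4.2 allows a more complete assessment in the same window to take priority. All of this stands.
- **Within-subscale proration is not exact either.** Parkinsonism items also differ among themselves. Suppose gait and postural instability are 4, the other eight parkinsonism items 1 and the rest 0, true total 16. With those two missing, the SAP rule gives 8/22 × 24 = 8.7 → 9 and within-subscale proration gives 1 × 10 = 10. The gain is small here, though it is in the right direction.
- **The SAP does not impute items.** That is correct as to its wording, and item and subscale scores stay missing. For the total, however, the identity above shows that the rule equals giving each missing item the mean of the rated ones.

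A reader might infer that the usual effect is to hide worsening, because gait and postural stability could be hard to test in frail subjects. Protocol 1.4 does mention frail, elderly patients, and bedridden subjects are excluded only at entry (Protocol 4.3). But Protocol 4.2 requires that subjects can attend the clinic, and nothing in the documents says which items go unrated or how often. The direction is therefore not established.

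**Conclusion.** The point holds as a minor weakness of a stated scoring rule. A subject's ESRS-A total can move by several points with no true change: −8 to +6 in the assumed profile with parkinsonism items at 3, and −6 to +4 with them at 2. Three conditions must hold together: item levels differ between subscales, missing items cluster in one subscale, and the pattern differs from that at Baseline. It does not follow that the study's extrapyramidal results will be biased, or in which direction. The group-level effect cannot be sized without a missing-item rate. Because the endpoint is exploratory and descriptive, with no hypothesis testing, no formal conclusion depends on it. The change is worth making because it is cheap.

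**What to change.** Replace the missing-item rule for the total in SAP 5.3.6 with:

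> When no more than 4 of the 24 items are missing and at least half of the items in every subscale are rated, each subscale sum is prorated as the mean of its rated items times its number of items. The total is the sum of the four, rounded to a whole number. In all other cases with missing items the total is not derived.

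State that these prorated sums serve only the total, so that listed subscale scores stay unimputed. Apply the same rule to antecedent-study visits in the combined double-blind and open-label displays, and report the number of prorated totals by visit.

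The cost is SAP wording and a few lines of code, with no new data. There are two downsides. A few totals that are now derived would become missing, for example with both akathisia items or four of six dystonia items unrated. Antecedent-study totals must also be re-derived for the combined tables. Any ESRS-A totals shown at the two interim analyses in SAP 16.1 would rest on the rule then in force, and a note should say so.

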5.3.7 MMSE

The MMSE is assessed at Baseline, Weeks 2, 4, 8, 12, 16, 28, 40 and Week 52/ET visits.

The MMSE is a 30-item questionnaire that includes simple questions and problems in the following areas: time and place of testing, repeating lists of words, arithmetic, language use

and comprehension, and copying or drawing. The MMSE is being used in this study to screen for cognitive impairment and as a safety measure.

Each of the 30 items has 2 possible values: 0=incorrect; 1=correct. The MMSE total score will be derived as the sum of the 30 item scores, thus the total score has a potential range of 0 to 30, with lower scores indicating more severe cognitive impairment.

If 6 or fewer items are missing, then the total score for a given subject and timepoint will be imputed as the mean of the non-missing items multiplied by 30 and rounded to the nearest integer. If more than 6 items are missing, the total score will not be imputed.

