6.3.6 Mini-Mental State Examination

The Mini-Mental State Examination (MMSE) is a brief 30-point questionnaire that is used to quantitatively assess cognition ([Folstein et al. 1975](#)). The MMSE includes simple questions and problems in a number of areas: the time and place of testing, repeating lists of words, arithmetic, language use and comprehension, and copying a drawing. The MMSE is being used in this study to screen for cognitive impairment and as a safety measure.

The MMSE will be administered at all scheduled visits.

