14.6.2 MMSE

The MMSE is assessed at Baseline, Weeks 2, 4, 8, 12, 16, 28, 40 and Week 52/ET visits.

The MMSE total score will be summarized using descriptive statistics at Baseline and scheduled post-Baseline visits. The change from Baseline scores will also be summarized at scheduled post-Baseline visits. The MMSE total score will be presented for OL timepoints only using OL Baseline, and DB+OL timepoints using the DB Baseline from the antecedent study (see [Section 5.2](#) and [Table 4](#)).

The individual item scores will be listed but not summarized.

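### The SAP prorates MMSE totals with 1 to 6 missing items whatever the reason, so items left blank because of impairment can add up to 6 points and hide a decline, or exaggerate one if the blanks are at Baseline.

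*SAP*

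**What the plan says.** SAP 5.3.7 defines the item scoring: "Each of the 30 items has 2 possible values: 0=incorrect; 1=correct". The total is the sum, from 0 to 30, "with lower scores indicating more severe cognitive impairment". The missing-item rule opens "If 6 or fewer items are missing, then the total score" and goes on to say that this total is "imputed as the mean of the non-missing items multiplied by 30 and rounded to the nearest integer". Above that limit no total is produced: "If more than 6 items are missing, the total score will not be imputed". The rule does not refer to the reason an item is missing.

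SAP 5.3 adds that where a total is also collected on the eCRF, the derived value is the one analysed; both appear in listings.

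On use, SAP 14.6.2 states "The MMSE total score will be summarized using descriptive statistics at Baseline and scheduled post-Baseline visits" and "The change from Baseline scores will also be summarized at scheduled post-Baseline visits". Change is shown from the OL Baseline and from the antecedent study's Baseline. Item scores appear only in listings. Protocol 6.3.6 gives the instrument's role: "The MMSE is being used in this study to screen for cognitive impairment and as a safety measure". Cognition is a named exploratory safety objective (Protocol 2.2, SAP 2.3), and the MMSE is the only scale listed for it (Protocol 2.2.1, SAP 2.3.1).

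**The concern.** Proration treats a missing item as if the subject would have done as well on it as on the rest. That is reasonable when the gap has nothing to do with ability. On a test of ability, a blank may itself be evidence of failure. The documents expect some loss of capacity during the study: a subject who can no longer reliably complete the C-SSRS moves to the GCAS (Protocol 6.3.5). The Baseline MMSE categories in SAP 8.2 reach down to 10 or below.

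The SAP does not ask why an item is missing, plans no alternative summary, and does not count prorated totals. A reader of the MMSE tables therefore could not tell whether a flat mean change reflects stable cognition or prorated blanks. If a site left an item blank but counted it as zero in its own total, the derived total would still replace the site's figure in every summary.

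The rule also sits oddly beside the SAP's other safety conventions. Missing AE severity becomes severe (5.5.4), missing causality becomes related (5.5.5), and unclear AE timing becomes treatment-emergent (5.5.3). Those resolve doubt in the cautious direction. The MMSE rule does not.

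**Working it through.** The plan states no figure to reproduce here: there is no hypothesis test and no powered sample size. The check applies the SAP rule directly.

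**Inputs (SAP 5.3.7).** 30 items scored 0 or 1; S = number correct among the items scored; m = number missing, 1 to 6.

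**Formulas.** Prorated total = round(30 × S / (30 − m)). The SAP says nearest integer; halves are assumed to round up. Total with missing items scored incorrect = S. Inflation before rounding = S × m / (30 − m).

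**All possible cases.** For each m, S runs from 0 to 30 − m.

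| m | Combinations | Prorated total above S | Smallest S with a rise | Largest rise |
|---|---|---|---|---|
| 1 | 30 | 15 | 15 | 1 |
| 2 | 29 | 22 | 7 | 2 |
| 3 | 28 | 23 | 5 | 3 |
| 4 | 27 | 23 | 4 | 4 |
| 5 | 26 | 23 | 3 | 5 |
| 6 | 25 | 23 | 2 | 6 |
| All | 165 | 129 | | 6 |

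The prorated total is never below S. It equals S in 165 − 129 = 36 combinations. These counts describe the rule, not how often each case would occur.

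**Blanks only after Baseline** (complete Baseline total of 20):

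| m | S | Prorated total | Change, missing = 0 | Change, SAP rule |
|---|---|---|---|---|
| 4 | 17 | 19.62 → 20 | −3 | 0 |
| 6 | 16 | 20 | −4 | 0 |
| 6 | 18 | 22.5 → 23 | −2 | +3 |

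**Blanks only at Baseline.** Baseline with 16 of 24 correct and 6 missing: prorated 20. Later complete form with 16 correct: 16. Change under the SAP rule is 16 − 20 = −4; with missing items scored 0 it is 16 − 16 = 0.

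**Same number of blanks at both visits.** Baseline 16 of 24 gives 20; later 12 of 24 gives 12 × 30/24 = 15. Change under the SAP rule is −5; with missing items scored 0 it is −4. Here proration enlarges the decline.

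**Effect on a visit mean.** The frequency of missing items is not in the documents. Assume, for illustration only, that 5% to 10% of totals at a visit are affected and Baseline is complete. With m = 6 and S = 16 the rise is 4 points, so the mean moves by 0.05 × 4 = 0.2 to 0.10 × 4 = 0.4. With m = 1 and S = 16 the rise is 16 × 1/29 = 0.55 before rounding and 1 after, so the mean moves by 0.05 to 0.10.

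**What the two scores bound.** The score the subject would have had with every item answered lies between S and S + m. Zero scoring is the lower limit. The prorated total lies inside the range: for S = 16 and m = 6 the range is 16 to 22 and the prorated total is 20.

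**The case against.** The strongest reply is that the rule acts only on items that are missing, and neither document says that an item the subject could not answer is recorded as missing rather than as 0. If sites enter 0, proration adds nothing. This stands, and it makes the inflation conditional. It does not close the point, because the SAP leaves the coding open.

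Second, zero is the lowest value an item can take, so any other imputation looks upward against it. Against true ability the error can go either way. This also stands. The MMSE includes copying or drawing, and Protocol 1.4 describes enrolment of subjects with Parkinson's disease. Scoring every blank 0 would turn motor or sensory limits into cognitive failures, so zero scoring should not simply replace proration for all blanks.

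Third, a reader might infer that inability to answer always raises the score and that the summaries are therefore biased towards no cognitive worsening. The documents do not support that. In 36 of 165 combinations there is no rise. The rule also acts at Baseline, where it works the other way. Nothing in either document shows blanks increasing over 52 weeks. Nor would a planned table show a subject moving into the 25 to 30 category at Week 52: SAP 8.2 uses the MMSE categories for OL Baseline only.

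Finally, the consequences are limited. The MMSE is exploratory and descriptive, TEAEs can also capture cognitive events, item listings allow prorated totals to be traced, and SAP 5.4.2 allows a more complete assessment to be preferred within a window. These points limit the importance of the concern. They do not make the effect visible in the tables.

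**Conclusion.** The point holds as a conditional weakness. If items are recorded as missing because the subject could not or would not answer, the SAP total exceeds the zero-scored total by up to 6 points. A fall of 4 points from a complete Baseline of 20 can then appear as no change. If such blanks are at Baseline, later decline is exaggerated instead. The net direction is therefore unknown, and a claim of systematic bias in favour of the drug would go beyond the documents.

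The conclusion rests on two things the documents do not give: how unanswered items are coded, and how often they occur at each visit. The illustrative mean shifts depend wholly on the assumed 5% to 10% frequency and a complete Baseline. What is certain is that the plan neither separates the reasons for missing items nor shows how much the MMSE summaries depend on proration. Correcting this is a cheap improvement, and it bears on what can be concluded about cognition.

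**What to change.** In SAP 5.3.7:

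- Score items refused or unanswered because of impairment as 0.
- Limit proration, within the existing limit of 6, to items missing for non-cognitive reasons: sensory, motor, or not administered.
- Where the reason is not recorded, present the by-visit and change-from-Baseline MMSE summaries twice: with missing items scored 0, and prorated. Apply each method at Baseline as well as later visits.
- Report the number of MMSE totals with any missing item, by visit and cohort.

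The cost is SAP wording, one extra derived variable and one extra table. The downside is that the zero-scored summary understates ability when blanks are non-cognitive; the prorated summary beside it shows how much the result depends on that choice. The pair should not be described as strict bounds, since the prorated total is not an upper limit.
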